## Appendix 6 Assessment of anti-tumor activity per RECIST v. 1.1

Assessment of tumor responses may be performed following the revised RECIST guidelines, version 1.1. Some of these definitions and criteria are highlighted below.

## Measurability of tumor baseline

- CT with intravenous (IV) contrast and MRI are the best currently available and reproducible methods to measure target lesions selected for response assessment. Conventional CT and MRI should be performed with cuts of 10 mm or less in slice thickness contiguously. Spiral CT should be performed using a 5 mm contiguous reconstruction algorithm.
- Standard imaging studies should be performed according to the imaging manual provided by the central imaging laboratory designated by the Sponsor.

## Definitions

At baseline, tumor lesions/lymph nodes will be categorized measurable or non-measurable as follows:

#### Measurable

*Tumor lesions:* Must be accurately measured in at least one dimension (longest diameter in the plane of measurement is to be recorded) with a minimum size of:

- 10 mm by CT scan (CT scan slice thickness no greater than 5 mm).
- 10 mm caliper measurement by clinical exam (lesions which cannot be accurately measured with calipers should be recorded as non-measurable).
- 20 mm by chest X-ray.

*Measurable malignant lymph nodes:* To be considered pathologically enlarged and measurable, a lymph node must be  $\geq 15$  mm in short axis when assessed by CT scan (CT scan slice thickness recommended to be no greater than 5 mm). At baseline and in follow-up, only the short axis will be measured and followed. See also notes below on 'Baseline documentation of target and non-target lesions' for information on lymph node measurement.

#### Non-measurable

All other lesions, including small lesions (longest diameter < 10 mm or pathological lymph nodes with  $\geq$  10 to < 15 mm short axis) as well as truly non-measurable lesions. Lesions considered truly non-measurable include: leptomeningeal disease, ascites, pleural or pericardial effusion, inflammatory breast disease, lymphangitic involvement of skin (nevi) or lung, and abdominal masses/abdominal organomegaly identified by physical exam that is not measurable by reproducible imaging techniques.

#### Special considerations regarding lesion measurability

Bone lesions, cystic lesions, and lesions previously treated with local therapy require particular comment:

#### Bone lesions

Bone scan, PET scan, or plain films are not considered adequate imaging techniques to measure bone lesions. However, these techniques can be used to confirm the presence or disappearance of bone lesions.

Lytic bone lesions or mixed lytic-blastic lesions, with identifiable soft tissue components, that can be evaluated by cross sectional imaging techniques such as CT or MRI can be considered as measurable lesions if the soft tissue component meets the definition of measurability described above.

Blastic bone lesions are non-measurable.

#### Cystic lesions

Lesions that meet the criteria for radiographically defined simple cysts should not be considered as malignant lesions (neither measurable nor non-measurable) since they are, by definition, simple cysts.

'Cystic lesions' thought to represent cystic metastases can be considered as measurable lesions, if they meet the definition of measurability described above. However, if noncystic lesions are present in the same patient, these are preferred for selection as target lesions.

#### Lesions with prior local treatment

Tumor lesions situated in a previously irradiated area, or in an area subjected to other locoregional therapy, are not considered measurable unless there has been demonstrated progression in the lesion.

#### Specifications by methods of measurements

#### Measurement of lesions

All measurements should be recorded in metric notation, using calipers if clinically assessed. All baseline evaluations should be performed as close as possible to the treatment start and NEVER more than 4 weeks before the beginning of the treatment.

#### Method of assessment

The same method of assessment and the same technique should be used to characterize each identified and reported lesion at baseline and during follow-up. Imaging-based evaluation should always be done rather than clinical examination unless the lesion(s) being followed cannot be imaged but are assessable by clinical exam.

*Clinical lesions:* Clinical lesions will only be considered measurable when they are superficial and  $\geq 10$  mm diameter as assessed using calipers (e.g., skin (nevi) nodules). For the case of skin (nevi) lesions, documentation by color photography including a ruler to estimate the size of the lesion is suggested. As noted above, when lesions can be evaluated by both clinical exam and imaging, imaging evaluation should be undertaken since it is more objective and may also be reviewed at the end of the study.

*Chest X-ray:* Chest CT is preferred over chest X-ray, particularly when progression is an important endpoint, since CT is more sensitive than X-ray, particularly in identifying new lesions. However, lesions on chest X-ray may be considered measurable if they are clearly defined and surrounded by aerated lung.

*CT, MRI:* CT is the best currently available and reproducible method to measure lesions selected for response assessment. This guideline has defined measurability of lesions on CT scan based on the assumption that CT slice thickness is 5 mm or less. When CT scans have a slice thickness greater than 5 mm, the minimum size for a measurable lesion should be twice the slice thickness. MRI is also acceptable in certain situations (e.g., for body scans).

## **Tumor response evaluation**

#### Assessment of overall tumor burden and measurable disease

To assess objective response or future progression, it is necessary to estimate the overall tumor burden at baseline and use this as a comparator for subsequent measurements. In this study, only patients with measurable disease at baseline should be included in the study.

### Baseline documentation of 'target' and 'non-target' lesions

When more than one measurable lesion is present at baseline, all lesions up to a maximum of five lesions total (and a *maximum* of two lesions per organ) representative of all involved organs should be identified as target lesions and will be recorded and measured at baseline (this means in instances where patients have only one or two organ sites involved, a maximum of two and four lesions respectively will be recorded).

Target lesions should be selected on the basis of their size (lesions with the longest diameter), be representative of all involved organs, but in addition should be those that lend themselves to reproducible repeated measurements. It may be the case that, on occasion, the largest lesion does not lend itself to reproducible measurement in which circumstance the next largest lesion which can be measured reproducibly should be selected.

*Lymph nodes* merit special mention since they are normal anatomical structures which may be visible by imaging even if not involved by tumor. As noted above, pathological nodes which are defined as measurable and may be identified as target lesions must meet the criterion of a short axis of  $\geq 15$  mm by CT scan. Only the short axis of these nodes will contribute to the baseline sum. The short axis of the node is the diameter normally used by radiologists to judge if a node is involved by solid tumor. Nodal size is normally reported as two dimensions in the plane in which the image is obtained (for CT scan this is almost always the axial plane; for MRI the plane of acquisition may be axial, sagittal, or coronal). The smaller of these measures is the short axis of 20 mm and qualifies as a malignant, measurable node. In this example, 20 mm should be recorded as the node measurement. All other pathological nodes (those with short axis  $\geq 10$  mm but < 15 mm) should be considered non-target lesions. Nodes that have a short axis < 10 mm are considered non-pathological and should not be recorded or followed.

A sum of the diameters (longest for non-nodal lesions, short axis for nodal lesions) for all target lesions will be calculated and reported as the baseline sum of the diameters. If lymph nodes are to be included in the sum, then as noted above, only the short axis is added into the sum.

The baseline sum of the diameters will be used as reference to further characterize any objective tumor regression in the measurable dimension of the disease.

All other lesions (or sites of disease) including pathological lymph nodes should be identified as non-target lesions and should also be recorded at baseline. Measurements are not required and these lesions should be followed as 'present', 'absent', or in rare cases 'unequivocal progression' (more details to follow). In addition, it is possible to record multiple non-target lesions involving the same organ as a single item on the case record form (e.g., 'multiple enlarged pelvic lymph nodes' or 'multiple liver metastases').

## **Response criteria**

This section provides the definitions of the criteria used to determine objective tumor response for target lesions.

#### Evaluation of target lesions

- *Complete Response:* Disappearance of all target lesions. Any pathological lymph nodes (whether target or non-target) must have reduction in short axis to < 10 mm.
- *Partial Response:* At least a 30% decrease in the sum of diameters of target lesions, taking as reference the baseline sum diameters.
- *Progressive Disease:* At least a 20% increase in the sum of diameters of target lesions, taking as reference the smallest sum on study (this includes the baseline sum if that is the smallest on study). In addition to the relative increase of 20%, the sum must also demonstrate an absolute increase of at least 5 mm. (Note: the appearance of one or more new lesions is also considered progression).
- *Stable Disease:* Neither sufficient shrinkage to qualify for PR nor sufficient increase to qualify for PD, taking as reference the smallest sum diameters while on study. In this study, the minimum duration for SD is defined as 8 weeks (± 2 days).

#### Special notes on the assessment of target lesions

*Lymph nodes.* Lymph nodes identified as target lesions should always have the actual short axis measurement recorded (measured in the same anatomical plane as the baseline examination), even if the nodes regress to below 10 mm on study. This means that when lymph nodes are included as target lesions, the 'sum' of lesions may not be zero even if complete response criteria are met, since a normal lymph node is defined as having a short axis of < 10 mm. For PR, SD, and PD, the actual short axis measurement of the nodes is to be included in the sum of target lesions.

*Target lesions that become 'too small to measure'*. While on study, all lesions (nodal and nonnodal) recorded at baseline should have their actual measurements recorded at each Response Criteria subsequent evaluation, even when very small (e.g., 2 mm). However, sometimes lesions or lymph nodes which are recorded as target lesions at baseline become so faint on CT scan that the radiologist may not feel comfortable assigning an exact measure and may report them as being 'too small to measure'. When this occurs, it is important that a value be recorded on the case report form. If it is the opinion of the radiologist that the lesion has likely disappeared, the measurement should be recorded as 0 mm. If the lesion is believed to be present and is faintly seen but too small to measure, a default value of 5 mm should be assigned

(Note: It is less likely that this rule will be used for lymph nodes since they usually have a definable size when normal and are frequently surrounded by fat such as in the retroperitoneum; however, if a lymph node is believed to be present and is faintly seen but too small to measure, a default value of 5 mm should be assigned in this circumstance as well). This default value is derived from the 5 mm CT slice thickness (but should not be changed with varying CT slice thickness). The measurement of these lesions is potentially non-reproducible, therefore providing this default value will prevent false responses or progressions based upon measurement error. To reiterate, however, if the radiologist is able to provide an actual measure, that should be recorded, even if it is below 5 mm.

Lesions that split or coalesce on treatment. When non-nodal lesions 'fragment', the longest diameters of the fragmented portions should be added together to calculate the target lesion sum. Similarly, as lesions coalesce, a plane between them may be maintained that would aid in obtaining maximal diameter measurements of each individual lesion. If the lesions have truly coalesced such that they are no longer separable, the vector of the longest diameter in this instance should be the maximal longest diameter for the 'coalesced lesion'.

#### Evaluation of non-target lesions

This section provides the definitions of the criteria used to determine the tumor response for the group of non-target lesions. While some non-target lesions may actually be measurable, they need not be measured and instead should be assessed only qualitatively at the time points specified in the protocol.

- *Complete Response:* Disappearance of all non-target lesions and normalization of tumor marker level. All lymph nodes must be non-pathological in size (< 10 mm short axis).
- *Non-CR/Non-PD:* Persistence of one or more non-target lesion(s) and/or maintenance of tumor marker level above the normal limits.
- *Progressive Disease:* Unequivocal progression (see comments below) of existing nontarget lesions. (Note: the appearance of one or more new lesions is also considered progression).

#### Special notes on the assessment of progression of non-target disease

The concept of progression of non-target disease requires additional explanation as follows:

When the patient also has measurable disease. In this setting, to achieve 'unequivocal progression' on the basis of the non-target disease, there must be an overall level of substantial worsening in non-target disease such that, even in the presence of SD or PR in target disease, the overall tumor burden has increased sufficiently to merit discontinuation of therapy (see further details below). A modest 'increase' in the size of one or more non-target lesions is usually not sufficient to quality for unequivocal progression status. The designation of overall progression solely on the basis of change in non-target disease in the face of SD or PR of target disease will therefore be extremely rare.

#### Evaluation of new lesions

The appearance of new malignant lesions denotes disease progression; therefore, some comments on detection of new lesions are important. There are no specific criteria for the identification of new radiographic lesions; however, the finding of a new lesion should be unequivocal: i.e., not attributable to differences in scanning technique, change in imaging modality or findings thought to represent something other than tumor (for example, some 'new' bone lesions may be simply healing or flare of pre-existing lesions). This is particularly important when the patient's baseline lesions show partial or complete response. For example, necrosis of a liver lesion may be reported on a CT scan report as a 'new' cystic lesion, which it is not.

A lesion identified on a follow-up study in an anatomical location that was not scanned at baseline is considered a new lesion and will indicate disease progression. An example of this is the patient who has visceral disease at baseline and while on study has a CT or MRI of the brain ordered which reveals metastases. The patient's brain metastases are considered to be evidence of PD even if he/she did not have brain imaging at baseline.

If a new lesion is equivocal, for example because of its small size, continued therapy and follow-up evaluation will clarify if it truly represents a new disease. If repeat scans confirm there is definitely a new lesion, then progression is to be declared using the date of the initial scan.

#### Evaluation of best overall response

The best overall response is the best response recorded from the start of the study treatment until the End of Treatment.

The patient's best overall response assignment will depend on the findings of both target and non-target disease and will also take into consideration the appearance of new lesions.

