#### 5.7 Discontinuation from the treatment or study

#### 5.7.1 Patient discontinuation from treatment

Patients will be removed from the study treatment at any time if they meet any of the following criteria:

- Documented radiographic progression of disease
  - Radiographic progression must be confirmed by central radiology prior to treatment discontinuation if progression is seen on the first or second posttreatment scan
  - Patients may remain on study treatment if, in the opinion of the Investigator and with the agreement of the Medical Monitor, they continue to derive benefit from derazantinib

- Central negative or unconfirmed FISH test result for an *FGFR2* fusion in patients enrolled based on a locally-documented *FGFR2* fusion positive
  - If the central FISH test could not be performed for technical reasons and the patient did not experience radiographic progression, the patient may be allowed to continue the study treatment
  - If the central FISH test result is negative for an *FGFR2* fusion, the patient should be discontinued from the study treatment, other than in exceptional cases when, based on ethical considerations and an individual benefit-risk assessment, discontinuation of the patient from the study treatment is considered unacceptable
- Documented clinical progression of disease
- Clinical unacceptable toxicities despite optimal treatment or dose reduction
- Pregnancy (see Section 8.8.2).
- Patient decision to discontinue treatment and study visits
- Withdrawal of consent from treatment and study follow up calls
- Non-compliance with any part of the study, as assessed by the Investigator or Medical Monitor
- Investigator's decision after discussion with the Medical Monitor or designee
- Death

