# 3.2.7.1 Analysis of Primary Efficacy Variable

#### **Substudy 1**

The primary efficacy endpoint for Substudy 1 will be ORR, defined as the achievement of confirmed CR or PR using RECIST v1.1(Eisenhauer 2009) as assessed by BICR.

Per protocol inclusion criteria, only patients with measurable disease by RECIST version 1.1 criteria should be enrolled. If a patient without measurable disease is enrolled, the ITT principle requires including these patients in the analyses. Hence, analyses will be based on patients with either measurable or non-measurable disease. For this purpose, non-CR/non-PD in patients with non-measurable disease will be considered equivalent to SD in patients with measurable disease, and the same rules will be applied.

Classification of best confirmed response is done according to the following hierarchy and rules:

- 1. CR: requires two consecutive CR response assessments a minimum of four weeks apart
- 2. PR: requires two consecutive PR response assessments OR a PR response followed by a consecutive CR response assessment (a minimum of four weeks apart)
- 3. SD: requires only one SD response assessment (provided minimum criteria for SD duration met)
- 4. Non-CR/Non-PD (non-measurable disease patients only): requires only one Non-CR/Non-PD response assessment (provided minimum criteria for Non-CR/Non-PD duration met)
- 5. PD: requires only one PD response assessment

The minimum duration for SD and Non-CR/Non-PD is defined as at least 6 weeks i.e. 42 days, where the duration is calculated from the start of treatment until the criteria of SD is met.

The classification as per RECIST 1.1 (Eisenhauer 2009) is summarized in Table 1 below.

Table 1	: Best	overall	response	when	confirmation	of	CR	and	PR	required
I GOIC I			response		communication	•••	~			i cquii cu

Overall response						
First time point	Subsequent time point	BEST overall response				
CR	CR	CR				
CR	PR	SD, PD or PR*				
CR	SD	SD provided minimum criteria for SD duration met, otherwise PD				
CR	PD	SD provided minimum criteria for SD duration met, otherwise PD				
CR	NE	SD provided minimum criteria for SD duration met, otherwise NE				
PR	CR	PR				
PR	PR	PR				
PR	SD	SD				
PR	PD	SD provided minimum criteria for SD duration met, otherwise PD				
PR	NE	SD provided minimum criteria for SD duration met, otherwise NE				
NE	NE	NE				

CR = complete response, PR = partial response, SD = stable disease, PD = progressive disease, and NE = inevaluable.

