\* If a CR is truly met at first time point, then any disease seen at a subsequent time point, even disease meeting PR criteria relative to baseline, makes the disease PD at that point (since disease must have reappeared after CR). Best response would depend on whether minimum duration for SD was met. However, sometimes 'CR' may be claimed when subsequent scans suggest small lesions were likely still present and in fact the patient had PR, not CR at the first time point. Under these circumstances, the original CR should be changed to PR and the best response is PR.

For patients with non-measurable disease, SD should be replaced by non-CR/Non-PD

If the best overall response has any special cases or difficulty from unexpected data, then these may be checked and discussed with the study team to decide which best overall response is best suited.

As specified in RECIST 1.1, repeated 'NE' time point assessments complicate best response determination. Should a CR/PR be followed by one or more NE response and then a CR/PR, then confirmed response would be achieved (as an example PR-NE-PR will be considered as a confirmed response).

Patients without efficacy assessments are considered non-responders, and included in the analysis.

Hypothesis testing (null hypothesis  $[H_0]$  versus alternative hypothesis  $[H_A]$ ) were performed at the interim and will be performed in the final analyses as specified below:

Null Hypothesis H0: ORR  $\leq 0.10$  and Alternative Hypothesis HA: ORR > 0.10

The hypothesis testing will be performed using exact test for binomial proportion at a one-sided 2.5% significance level. Point estimates and exact 2-sided 95% confidence intervals (Clopper-Pearson) will be provided. If the p-value is  $\leq$  to 2.5% (one-sided), or equivalently the lower limit of the confidence interval is > 10%, the null hypothesis will be rejected.

Considering the number of patients per site planned in this study, the site effect and treatment by site interaction will not be evaluated.

#### Substudy 2

The primary efficacy endpoint for Substudy 2 will be the proportion of patients who have PFS at 3 months from the first date of receiving study drug as assessed by survival status or central radiology review RECIST 1.1.

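### No rule ends Substudy 1 best response at first central progression, so a PD-PR-PR sequence would count in the pivotal ORR; separately, the NE rule conflicts with the SAP's best-response table on CR-NE-PR.

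*Protocol*

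**What the plan says.** **Endpoint.** SAP 3.2.7.1: "The primary efficacy endpoint for Substudy 1 will be ORR, defined as the achievement of confirmed CR or PR" by RECIST 1.1 as read by BICR.

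**Response window.** Protocol Appendix 6, in its part on response evaluation, states: "The best overall response is the best response recorded from the start of the study treatment until the End of Treatment". The SAP's list of changes from the planned analysis (section 4) does not alter this window.

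**Treatment after progression.** Radiographic progression is a reason to stop under Protocol 5.7.1, with an exception: "Patients may remain on study treatment if, in the opinion of the Investigator and with the agreement of the Medical Monitor", the patient is judged still to benefit. Central confirmation of progression before stopping is required only when progression is seen on the first or second scan, and under Protocol 3.1 it follows a PD call by the investigator.

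**Classification.** SAP 3.2.7.1: "Classification of best confirmed response is done according to the following hierarchy and rules". The order is CR, PR, SD, Non-CR/Non-PD, PD. For the two categories that matter here: "PR: requires two consecutive PR response assessments" (or PR then CR, at least four weeks apart), and "PD: requires only one PD response assessment". The best-response table (Table 1 of that section) has no row that begins with PD.

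**NE scans.** Same section: "Should a CR/PR be followed by one or more NE response and then a CR/PR, then confirmed response would be achieved". The only worked example is PR-NE-PR. The table's CR-then-PR row gives SD, PD or PR. Its footnote says that after a true CR "any disease seen at a subsequent time point, even disease meeting PR criteria relative to baseline, makes the disease PD at that point"; PR applies only if the original CR is recoded.

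**The concern.** Nothing in the SAP says that PD ends the sequence of assessments eligible for best response. The protocol sets a window that runs past PD whenever treatment does. A later pair of PRs then outranks the earlier PD, and the patient enters the numerator of the pivotal endpoint.

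The endpoints would then disagree within one patient. SAP 3.2.7.1 makes the first BICR progression a PFS event, so the event would precede the response. SAP 3.2.7.2.2 runs DoR from first response to BICR progression, and here a progression has already occurred, so it is unclear which one ends the interval. DCR inherits the gap, because it uses the same hierarchy.

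The NE sentence is a second and independent problem. An unevaluable scan between a CR and a PR should not turn a sequence that the table treats as unresolved into a confirmed response. Special cases of best response may go to the study team for discussion, and the study is open label, so it is better to settle the rule in advance.

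**Working it through.** **1. What the rules do with each sequence**

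| BICR sequence | Literal result | Conflict |
|---|---|---|
| PD-PR-PR (PRs ≥4 weeks apart) | Confirmed PR | PFS event precedes the response; end of DoR unclear |
| PR-PD-PR | Not confirmed, because the PRs are not consecutive | None |
| PD by a new lesion that persists | Stays PD (Appendix 6 time-point table) | None |
| CR-NE-PR | Confirmed by the NE sentence | CR-then-PR row gives SD, PD or PR, with PR only after recoding |

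A patient can reach PD-PR-PR in two ways. One is the exception in Protocol 5.7.1. The other is a BICR PD that the investigator did not call: treatment and scans continue, and the documents do not say that central reading stops.

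**2. Reproducing the design (Protocol 10.7, SAP 1.4)**

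Inputs: null ORR 0.10, alternative 0.23, one-sided 0.025, exact binomial test, N = 100, stop if 4 or fewer of 40.

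- Futility: P(X ≤ 4 | n = 40) = 62.9% at 0.10 and 3.1% at 0.23. The plan states 63% and 3%.
- Boundary: P(X ≥ 16 | 100, 0.10) = 0.0399, Clopper-Pearson lower limit 9.4%, not rejected. P(X ≥ 17 | 100, 0.10) = 0.0206, lower limit 10.2%, rejected.
- With the futility look, P(reject | p) = Σ (x = 5 to 40) b(x; 40, p) · P(Bin(60, p) ≥ 17 − x). This is 0.0189 at p = 0.10 and 92.5% at p = 0.23. The stated power is about 90%; the same exact test at N = 96 to 98 gives 90.0% to 91.4%.

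**3. If such sequences add responders**

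The documents give no rate, so the increment e is an assumption. Put p = 0.10 + e in the same formula:

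| e (percentage points) | P(reject), planned 4/40 look | P(reject), no look |
|---|---|---|
| 0 | 0.0189 | 0.0206 |
| 0.5 | 0.029 | 0.031 |
| 1 | 0.042 | 0.046 |
| 2 | 0.081 | 0.087 |

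SAP 1.4 reports that the interim was held at 29 patients, with 6 responses, so the middle column describes the planned design.

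**4. When extra responders change the result**

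One extra responder matters only at exactly 16 of 100; two matter at 15 or 16. Single-stage binomial probabilities, n = 100:

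| True ORR | P(X = 16) | P(X = 15 or 16) |
|---|---|---|
| 0.10 | 1.9% | 5.2% |
| 0.15 | 10.4% | 21.5% |
| 0.20 | 6.4% | 11.2% |
| 0.23 | 2.4% | 3.9% |

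**The case against.** The best defence is that the path is narrow. Stopping at radiographic PD is the rule, and staying on treatment needs the Medical Monitor's agreement. Appendix 6 schedules tumor measurement until progression. Equivocal progression is followed to the next scan before it is declared. A persisting new lesion keeps the time point at PD, and a PR needs a 30% fall from baseline on two consecutive central reads. Appendix 6 presents itself as highlights of RECIST, and the SAP classifies response by RECIST 1.1. On CR-NE-PR, the footnote speaks of any subsequent time point, and the objective responses that the documents report in fusion-positive disease are PRs (6 of 29 in the earlier study, 6 of 29 at the interim), so a sequence starting with CR should be unusual.

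This stands as an argument about frequency. It does not supply the missing rule. The measurement schedule limits imaging, not which assessments count, and Protocol 6.9 sets on-treatment scans without that limit. A general citation of RECIST does not displace a window that the protocol states in its own words.

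Four stronger readings are tempting, and the documents do not support them:

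- A reader might infer that the End of Treatment window causes the CR-NE-PR problem. It does not; the NE sentence does, and the conflict would remain if response stopped at PD.
- A reader might infer that the table normally treats CR then PR as PD. It lists SD, PD or PR, and the footnote allows either reading of the first CR.
- A reader might infer that responses under new anticancer therapy also count. The window closes at End of Treatment, and Protocol 7.7.2 prohibits concurrent anticancer therapy, apart from limited palliative radiotherapy with treated lesions left out of assessment. This is largely covered.
- A reader might infer that DoR is undefined after PD. SAP 3.2.7.2.2 still gives a start and types of end; what is ambiguous is which progression applies.

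**Conclusion.** The point holds as a gap in the definition of the pivotal endpoint. By the stated window and the SAP hierarchy, PD-PR-PR counts as a confirmed response. By the NE sentence, CR-NE-PR does too, against the table. The second is an unresolved conflict between two rules, not a settled rule that such patients count.

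The likely effect is small. The rejection probabilities of 0.029, 0.042 and 0.081 rest on assumed increments of 0.5, 1 and 2 percentage points at a true ORR of 10%. A reader might take them as evidence that the type I error is in fact above 0.025; they are not, because no rate is documented. Near the design alternative the issue seldom matters: one extra responder changes the decision with probability 2.4% at a true ORR of 0.23, and at most 10.4% among the values examined (at 0.15). It merits correction because the correction is cheap and the boundary is one patient wide, not because the primary analysis is unsound.

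**What to change.** In SAP 3.2.7.1:

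1. State that only BICR assessments up to and including the first BICR PD count toward confirmed best overall response, and apply the same rule to ORR, DCR and DoR.
2. Restrict confirmation across NE scans to PR-NE-PR, PR-NE-CR and CR-NE-CR, and send CR-NE-PR to the CR-then-PR row of the table.

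Align the best-overall-response wording in Protocol Appendix 6, or record the difference in SAP section 4.

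The cost is one or two SAP sentences. Sample size, decision boundary and power calculation do not change. ORR may be slightly lower and cannot rise; any excluded post-progression responses can be listed or shown in a sensitivity analysis. The change concerns only which assessments are counted. It does not affect whether patients are treated beyond progression, which is a clinical matter and is not judged here.
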